**BACKGROUND**

**Purpose of Research**

KDH Research & Communication (KDHRC) received funding from the National Institutes of Health (NIH) National Institute on Minority Health and Health Disparities (NIMHD) to develop and evaluate Guardians Receiving Information through Navigators (GRIN). GRIN is an online professional development course that aims to prepare community health workers (CHWs), trusted community members familiar with their communities' needs and resources, to provide oral health outreach to low-income Black guardians of children and adolescents (henceforth, Black guardians).

In Phase I, KDHRC will convene a steering committee to inform an architecture plan that includes the full course content outline, video storyboards, and virtual interactive learning experience storyboards. Then, KDHRC will develop the GRIN prototype with two full course modules with text, video animatics, and rough-cut virtual client experiences. Finally, KDHRC will conduct a feasibility evaluation study (henceforth, study) to explore changes in CHWs' knowledge, attitudes, beliefs, perceived self-efficacy, and intentions to conduct oral health outreach to low-income Black guardians of children and adolescents after exposure to the GRIN prototype. This study will provide insight for future GRIN expansion, finalization, and randomized control trial (RCT) evaluation to measure behavior change among CHWs and guardians in a small business innovation research (SBIR) Phase II project.

Specifically, KDHRC proposes to conduct a two-group, randomized pretest/posttest feasibility study to evaluate the extent to which the GRIN prototype increases CHWs' knowledge, attitudes and beliefs, perceived self-efficacy, and intentions to conduct oral health care outreach to low-income Black guardians. KDHRC will conduct the study with CHWs nationwide.

The study will consist of pretest and posttest surveys and a virtual education session with two GRIN modules (treatment) or no intervention (control), pending Institutional Review Board (IRB) approval. The participants in the study are CHWs. KDHRC will partner with community-based organizations (CBOs) to assist with CHW recruitment.

**Terminology**

- CBO: Community-based organizations serving low-income Black guardians (e.g., National Association of Community Health Workers)
- Potential participants: CHWs recruited through CBOs
- Participants: CBO-recruited CHWs with completed consent forms

---

 CHWs include community health workers (CHWs), community health representatives (CHRs), lay health workers, and other titles.

This protocol describes the procedures for the study.

### **Responsible Parties**

[name], is the Principal Investigator with oversight of the GRIN project. [name], KDHRC's senior research associate, is the Project Director. [name], a KDHRC researcher, will manage the study.

Specifically, KDHRC will:

- Contract and share study materials with CBOs (recruitment subcontractors) to recruit participants
- Program and manage the online eligibility and consent forms, pretest survey, and posttest survey
- Send follow-up communications to consented participants
- Manage, clean, and analyze data
- Manage incentive distribution
- Report on study findings

KDHRC will contract with CBOs serving low-income Black guardians to be the recruitment subcontractors. To be eligible, each CBO must demonstrate organization stability and their capacity to participate in the study by having:

- (1) Federal nonprofit tax-exempt status under Section 501(c)(3) of the Internal Revenue Code
- (2) Internet access to share the recruitment materials with their network of CHWs
- (3) At least one active program that conducts health care outreach to low-income Black clients with a minimum of 15 active CHWs on staff (paid or volunteer)
- (4) A dedicated point of contact (POC) who will participate in a kick-off call with KDHRC and oversee the study at their CBO

Prior to sharing the study materials with each CBO, KDHRC will schedule a kick-off call with each CBO POC. During each kick-off call, KDHRC will briefly explain the study and provide an overview of the study requirements, time commitment, and consent process.

Each CBO will share the KDHRC-developed and IRB approved recruitment materials (e.g., flyer, email template) with potential participants.

## **RESEARCH DESIGN**

### **Goal**

The goal of the GRIN study is to examine the impact of the GRIN online professional development course prototype. Specifically, the study aims to address the following research question: "To what extent does the GRIN prototype increase CHWs' knowledge, attitudes and beliefs, perceived self-efficacy, and intentions to conduct oral health care outreach to low-income Black guardians of children and adolescents?"

### **Approach**

The study will use a two-group, pretest/posttest design. KDHRC will program the eligibility and consent forms, pretest survey and posttest surveys in Alchemer (formerly SurveyGizmo), a

secure online survey platform. This Phase I SBIR requires KDHRC to create content for two modules only: “Tooth decay impact on children and adolescents” and “Preventive oral health care.” Each module will be 20 – 30 minutes to complete and cover several expert-approved and reviewed topics. The participants in the intervention group will be sent a link to a KDHRC webpage where they will access the videos. Participants will access the videos by computer or cell phone to begin their virtual education session.

CHWs will be recruited through the CBOs and directed to an online link for eligibility screening and informed consent. KDHRC will confirm consent for each participant and after confirming consent, KDHRC will randomize each participant with completed consent into the treatment or control group using a 1:1 randomization. KDHRC will alternate assigning each participant with completed consent to the treatment group or the control group. Then, KDHRC will send each participant the link to the online pretest survey. After completing the pretest survey, each treatment group participant will receive access to a virtual education session with two GRIN modules. The control group will not receive an intervention. Each participant will receive the posttest survey two weeks after completing the pretest survey.

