### **Participants and recruitment**

CBOs with signed contracts to participate in the study will designate a POC who will be responsible for sharing recruitment materials with potential participants at their respective CBO. KDHRC will require each CBO to participate in a kick-off call with KDHRC staff during which time KDHRC staff will review the study protocol and answer additional questions. After the call, each CBO will be required to sign and return the certification form (see **Attachment X**) that states that the CBO POC understands the process and will follow the procedures outlined during the kick-off call. KDHRC will send the certification form via email or DocuSign to the CBO POC to sign prior to the CBO receiving the recruitment materials. If the CBO POC fails to follow the provisions of the certification form, the CBO will be removed from the study and will not receive full compensation.

CBOs will recruit potential participants in their networks, including potential participants within their CBOs, by sharing KDHRC-developed and IRB-approved recruitment materials (e.g., email template, flyer) thru email (e.g., listservs) and message boards. The recruitment materials will contain the link to the eligibility form, information on the time commitment, and instructions to contact KDHRC with questions. The study will include up to 120 CHWs nationwide (60 treatment, 60 control) from up to 16 CBOs. Although CBOs will recruit participants and may have access to potential participant information (e.g., name, email address) from their listservs, CBOs will not have knowledge of who actually serves as study participants and will not have access to enrolled participants’ data. KDHRC will remind participants that participation in the study is completely voluntary, that the CBO that shared recruitment materials with the participant will not have knowledge of who actually serves as study participants, and that his or her participation is no way tied to his or her position at and/or relationship with the CBO that shared recruitment materials with him or her.

Eligibility criteria for CHWs include:

- Must be at least 18 years old
- Must self-identify as a community health worker

- Must conduct outreach to Black clients

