## **Methods**

Upon completing and submitting the consent form to participate, each participant will be randomly assigned to either the treatment group or the control group. Then, KDHRC will send each participant the link to the online pretest survey. Participants will have two weeks to complete the pretest survey. A KDHRC researcher will send approximately three reminders (email, phone, text) per week to each consented participant to complete the pretest survey.

KDHRC will email the treatment group participants the information to access a virtual education session. When each participant accesses the virtual education session for the first time, each participant will be prompted to create a user ID and password and provide the last two letters of his or her last name, his or her three letter initials, and his or her year of birth, to access the virtual education session. Participants in the treatment group will have two weeks to complete the virtual education session. Participants in the control group will not receive an intervention for the two weeks between surveys. KDHRC will send one reminder (email or phone) per week to participants to promote continued engagement with the study (e.g., remind treatment participants to complete the virtual education session; remind control participants of the date when they will receive their posttest survey).

Then, two-weeks after pretest completion, KDHRC will email all participants the links and instructions for posttest survey completion. Each participant will have two weeks to complete the posttest survey. A KDHRC researcher will send approximately three reminders (email, phone, text) per week to each consented participant to complete the posttest survey.

The links to the pretest and posttest surveys will be used to collect participant data, therefore only KDHRC staff will have access to raw data. Each survey will take no more than 45 minutes to complete.

---

 We provide an additional incentive for treatment participants because treatment participants will access a virtual education session with two GRIN modules while the control group does not have to access anything.

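### The study is called randomized, but the only assignment method given is alternation, so 119 of 120 assignments are predictable and no concealment is described

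*Protocol*

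**What the plan says.** Three places in the protocol describe chance assignment:

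- Purpose of Research calls the study a "two-group, randomized pretest/posttest feasibility study".
- Approach says that "after confirming consent, KDHRC will randomize each participant with completed consent into the treatment or control group using a 1:1 randomization".
- Methods says: "Upon completing and submitting the consent form to participate, each participant will be randomly assigned to either the treatment group or the control group".

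The sentence in Approach that directly follows the word randomization gives the procedure: "KDHRC will alternate assigning each participant with completed consent to the treatment group or the control group". No other mechanism appears in either document. The SAP has no allocation section. Its binomial parameter of 0.5, under Power estimate and effect size, is an input to the power model.

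KDHRC is funded "to develop and evaluate Guardians Receiving Information through Navigators (GRIN"), confirms consent and assigns the arm (Approach), and will "Manage, clean, and analyze data" (Responsible Parties). The only masking statement concerns the recruiting organizations: "CBOs will not have knowledge of who actually serves as study participants" (Participants and recruitment, repeated under Identifying Information).

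**The concern.** Random assignment and alternation are incompatible descriptions of one step, and that step defines the design. A 1:1 ratio does not reconcile them, because it says how many go to each arm and not how the arm is chosen.

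Under alternation, anyone who knows the last assignment knows the next. The staff who know it also control when a consent counts as confirmed. Approach assigns after KDHRC confirms consent, while Methods assigns when the form is submitted. So the documents do not settle whether submission order or staff processing order drives the sequence. If processing order does, a staff member with two consents waiting could decide which one goes to treatment.

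The research question under Goal asks to what extent GRIN increases the outcomes, and that needs comparable arms. Purpose of Research adds that the results will inform a Phase II randomized trial. A report that called this study randomized would misdescribe it.

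**Working it through.** **1. The plan's own split.** The sequence T, C, T, C, … of length 120 gives 60 treatment and 60 control. This matches the protocol (Participants and recruitment) and the SAP (Number of subjects), so alternation meets the stated 1:1 ratio.

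**2. Predictability.** With one list, each assignment after the first is fixed by the one before, so the predictable share is (N − 1)/N. Enrolment is up to 120 and may be extended (Data Collection).

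| N | Predictable | Share |
|---|---|---|
| 60 | 59 | 98.3% |
| 90 | 89 | 98.9% |
| 120 | 119 | 99.2% |

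A single list is the plain reading, since no strata are stated. A separate list for each of 16 organizations would leave 120 − 16 = 104 predictable.

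For comparison, suppose a guesser sees all past assignments and always names the arm that is behind. Out of 120, the expected correct guesses are 60 (50%) under simple randomization, about 66 (55%) under one random ordering of 60/60, and about 82 (68%) under permuted blocks of 4, 6 and 8.

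**3. What staff know at assignment.** After the assignment step, Approach continues: "Then, KDHRC will send each participant the link to the online pretest survey". No outcome score exists when the arm is set. The documents show staff holding only eligibility and consent answers and contact details.

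**4. What the planned analyses would do with an imbalance.** With two time points, the condition-by-time test in a repeated measures ANOVA is a comparison of change scores, and a stable baseline difference cancels. Pretest-adjusted regression removes a share about equal to the pre-post correlation.

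**5. Illustration, all inputs assumed.** There are 60 consecutive pairs and no treatment effect. In a share s of pairs, the more engaged member is sent to treatment. Engagement is standard normal, so the expected difference within a steered pair is 1.128. Engagement correlates ρ with each score, and the pre-post correlation is r. Then

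adjusted bias ≈ s × 1.128 × ρ × (1 − r), in pretest SD units.

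- Smallest: 0.1 × 1.128 × 0.3 × 0.2 = 0.007 (simulated 0.007; rejection 5.1%).
- Largest: 0.2 × 1.128 × 0.7 × 0.6 = 0.095 (simulated 0.098; rejection 9.0%).
- Change scores, all 18 cells: bias within 0.003; rejection 4.8-5.3%.

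If engagement also drives gain (assumed 0.2 SD per SD), adjusted regression gives 0.028-0.120 SD and 5.4-10.1% rejection. Change scores then give 0.022-0.046 SD and 5.1-7.1%. Each cell used 20,000 replicates, with a nominal false-positive rate of 5%.

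**The case against.** The strongest reply is that little harm is likely. Steering needs two consents waiting at once and prognostic information that staff are not shown to have. Participants consent online themselves, the recruiting organizations do not know who enrols, the first-named analysis cancels stable differences, and this is a Phase I feasibility study. All of that stands, and it is why no bias is claimed.

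The illustration can also be criticized. Its largest cell pairs ρ = 0.7 with r = 0.4. Engagement alone would imply r = 0.7² = 0.49, so that cell needs a negative partial correlation: (0.40 − 0.49)/(1 − 0.49) = −0.18. Cells with a partial correlation near 0.2 give less:

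- ρ = 0.7, r = 0.6: 0.2 × 1.128 × 0.7 × 0.4 = 0.063 SD.
- ρ = 0.5, r = 0.4: 0.2 × 1.128 × 0.5 × 0.6 = 0.068 SD.

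Both reject about 7% of the time. About 0.07 SD and 7% is therefore a fairer upper end without engagement-driven gain. With that gain, a repeat simulation of the same two cells gave 0.087 and 0.102 SD, with 8.3% and 8.7% rejection. The SAP also plans baseline and demographic controls, which could remove more. They are not listed, so the amount is unknown.

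Finally, if relabelling is an acceptable remedy, the compulsory part is arguably only a label. That is partly right. What must be corrected is the mismatch between label and method, and either side can move. But relabelling leaves the predictability in place, so the limitation must then be stated.

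**Conclusion.** The concern holds and must be fixed. Three places claim randomization, the only method given is alternation, and no text elsewhere cures the contradiction. On the plain single-list reading, 119 of 120 assignments are known once the first is known. Nothing conceals the next arm from the KDHRC staff who confirm consent and assign.

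The size of any resulting bias cannot be derived from the documents. The simulated figures depend on assumed steering, correlations and gain, and on information staff are not shown to hold. They indicate a modest bias at most and do not carry the conclusion. Neither change scores nor pretest adjustment makes the design label correct.

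**What to change.** **If assignment can still be changed**, replace the alternation sentence in Approach with:

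> *Assignments follow a computer-generated 1:1 permuted-block sequence with varying block sizes, generated before the first consent, built to close at 60/60 at 120 participants, and extended with further blocks for any additional participants. The list is held by an existing KDHRC team member who does not confirm consents, and each assignment is released only after the consent is confirmed and logged.*

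Keep the block sizes out of the protocol. Align Methods so that assignment follows confirmation and logging of consent, not submission of the form.

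One such list has six blocks of 4, eight of 6 and six of 8 in random order (24 + 48 + 48 = 120). In 4,000 replicates it closed at 60/60, with a largest mid-block imbalance of 4 and 68.1% correct guesses. A single random ordering of 60/60 is harder to guess (about 55%). Blocks are preferred here because enrolment may stop short of 120 or be extended, and they keep the arms close throughout.

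**If alternation is kept or has already been used**, change the label in all three places. Purpose of Research should say quasi-randomized (alternation). Approach and Methods should say that participants are assigned 1:1 by alternation. Add to the report: *Assignment was by alternation, so the next arm was predictable and selection at entry cannot be excluded.*

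**Cost.** The first route needs edits to two protocol sections, IRB review, a list holder and a release step that slightly delays the pretest link. Responsible Parties names three KDHRC roles but does not say who confirms consents, so the separation must be arranged. The holder would still be KDHRC staff, and some guessability remains. The second route needs wording changes in three sections and leaves the predictability as it is. Neither changes the sample size, surveys, incentives or intervention. The later Phase II randomized trial is unaffected.

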### **Participants and recruitment**

CBOs with signed contracts to participate in the study will designate a POC who will be responsible for sharing recruitment materials with potential participants at their respective CBO. KDHRC will require each CBO to participate in a kick-off call with KDHRC staff during which time KDHRC staff will review the study protocol and answer additional questions. After the call, each CBO will be required to sign and return the certification form (see **Attachment X**) that states that the CBO POC understands the process and will follow the procedures outlined during the kick-off call. KDHRC will send the certification form via email or DocuSign to the CBO POC to sign prior to the CBO receiving the recruitment materials. If the CBO POC fails to follow the provisions of the certification form, the CBO will be removed from the study and will not receive full compensation.

CBOs will recruit potential participants in their networks, including potential participants within their CBOs, by sharing KDHRC-developed and IRB-approved recruitment materials (e.g., email template, flyer) thru email (e.g., listservs) and message boards. The recruitment materials will contain the link to the eligibility form, information on the time commitment, and instructions to contact KDHRC with questions. The study will include up to 120 CHWs nationwide (60 treatment, 60 control) from up to 16 CBOs. Although CBOs will recruit participants and may have access to potential participant information (e.g., name, email address) from their listservs, CBOs will not have knowledge of who actually serves as study participants and will not have access to enrolled participants’ data. KDHRC will remind participants that participation in the study is completely voluntary, that the CBO that shared recruitment materials with the participant will not have knowledge of who actually serves as study participants, and that his or her participation is no way tied to his or her position at and/or relationship with the CBO that shared recruitment materials with him or her.

Eligibility criteria for CHWs include:

- Must be at least 18 years old
- Must self-identify as a community health worker

- Must conduct outreach to Black clients
- Must have six months of field experience. KDHRC defines “field experience” as conducting outreach activities in their community, for example, working with clients in a clinic, conducting home visits, or educating clients at health fairs or community events
- Must be an active CHW. KDHRC defines “active” as conducting outreach activities, such as working with clients in a clinic, conducting home visits, or educating clients at health fairs or community events, in the last six months
- Must have Internet access either at home or at work to access the GRIN virtual education session and/or online surveys.

Each participant in both the treatment group and the control group will receive a \$25 e-gift card (Amazon or Walmart) incentive after completing the pretest survey, and a \$25 e-gift card (Amazon or Walmart) incentive after completing the posttest survey for a total of up to \$50 in e-gift card incentives (Amazon or Walmart). Each participant in the treatment group will receive an additional \$25 incentive for completing the virtual education session with two GRIN modules.

## **Methods**

Upon completing and submitting the consent form to participate, each participant will be randomly assigned to either the treatment group or the control group. Then, KDHRC will send each participant the link to the online pretest survey. Participants will have two weeks to complete the pretest survey. A KDHRC researcher will send approximately three reminders (email, phone, text) per week to each consented participant to complete the pretest survey.

KDHRC will email the treatment group participants the information to access a virtual education session. When each participant accesses the virtual education session for the first time, each participant will be prompted to create a user ID and password and provide the last two letters of his or her last name, his or her three letter initials, and his or her year of birth, to access the virtual education session. Participants in the treatment group will have two weeks to complete the virtual education session. Participants in the control group will not receive an intervention for the two weeks between surveys. KDHRC will send one reminder (email or phone) per week to participants to promote continued engagement with the study (e.g., remind treatment participants to complete the virtual education session; remind control participants of the date when they will receive their posttest survey).

Then, two-weeks after pretest completion, KDHRC will email all participants the links and instructions for posttest survey completion. Each participant will have two weeks to complete the posttest survey. A KDHRC researcher will send approximately three reminders (email, phone, text) per week to each consented participant to complete the posttest survey.

The links to the pretest and posttest surveys will be used to collect participant data, therefore only KDHRC staff will have access to raw data. Each survey will take no more than 45 minutes to complete.

---

 We provide an additional incentive for treatment participants because treatment participants will access a virtual education session with two GRIN modules while the control group does not have to access anything.

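### Allocation is called a 1:1 randomization but is carried out by alternation, so staff who confirm consent can predict the next arm

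*Protocol*

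**What the plan says.** The Protocol's Approach section labels the allocation a 1:1 randomization and states when it happens: "KDHRC will confirm consent for each participant and after confirming consent, KDHRC will randomize each participant with completed consent". It then states how: "KDHRC will alternate assigning each participant with completed consent to the treatment group or the control group". The Methods section gives the same timing but a different mechanism: "Upon completing and submitting the consent form to participate, each participant will be randomly assigned to either the treatment group or the control group". The Purpose of Research section also calls the design randomized.

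The pretest link goes out after allocation. On the window, Methods says "Participants will have two weeks to complete the pretest survey". On contact during it: "A KDHRC researcher will send approximately three reminders (email, phone, text) per week to each consented participant to complete the pretest survey". The arm is not acted on until the pretest is in: "After completing the pretest survey, each treatment group participant will receive access to a virtual education session with two GRIN modules". The posttest is timed from the same event: "Each participant will receive the posttest survey two weeks after completing the pretest survey".

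Neither document describes a generated sequence, concealment of it, or blinding of the staff who send reminders. In the SAP (Statistical methods for outcome measures), the pretest is one of the two time points in the repeated measures ANOVA and the first block entered in the regressions.

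**The concern.** Two descriptions of one step cannot both hold. If staff alternate, the assignment is deterministic and the word random is wrong. If assignment is random, the alternation sentence is wrong. As written, the only operational instruction is alternation.

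A predictable sequence lets anyone who handles consent confirmations know which arm the next CHW will enter. Confirming sooner, later or not at all could then depend on the arm, even without intent.

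Timing adds a second, weaker exposure. The arm exists for up to two weeks before baseline is measured, while KDHRC is in contact with the CHW. Three of the four outcomes (attitudes and beliefs, self-efficacy, intentions) are survey self-ratings that knowledge of the arm could colour. Treatment CHWs can also earn an extra $25 for the course, so a CHW who learned the arm early would face different pay and burden when deciding whether to start. A CHW who never submits a pretest is lost after allocation, because both SAP analyses use the pretest.

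**Working it through.** The plan gives no figure for predictability, pretest non-start or pre-post correlation, so there is no stated result to reproduce. Its only relevant numbers are 120 CHWs, 60 per group, a two-week pretest window and about three reminders a week. Everything else below is labelled as an assumption.

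**1. Predictability of the next arm**, for someone who knows all past assignments:
- Alternation: 100%.
- Simple 1:1 randomization: 50%.
- Permuted blocks of 4, block size known: expected correct guesses are 1/2 + 2/3 + 2/3 + 1 = 2.83 out of 4, or 71%.
- Permuted blocks of 8, block size known: 67% by the same method.

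Varying the block size and hiding the list makes prediction harder than the last two figures suggest.

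**2. Balance.** Under simple randomization of 120, the chance of exactly 60/60 is C(120,60)/2^120, about sqrt(2/(π × 120)) = 0.073, or about 7%. Blocks are therefore needed to stay near 60/60. With blocks of at most 8, the arms can differ by no more than 4.

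**3. Contact before baseline.** 3 reminders a week × 2 weeks = about 6 for a CHW who uses the full window.

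**4. Analysable number.** With 120 consents and assumed non-start of 10%, 20% or 30%, 120 × 0.9, 0.8 or 0.7 = 108, 96 or 84 CHWs have a pretest (54, 48 or 42 per group if split evenly). This holds whether allocation precedes or follows the pretest. Only if 120 pretest completers were wanted would consents have to rise, to 120/0.9, 120/0.8 or 120/0.7 = 134, 150 or 172.

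**5. How large a timing bias could be.** Assumptions: pre-post correlation r of .5 to .7; non-start differing between arms by 10 to 20 points; non-starters differing from starters by 0.25 to 0.5 SD.
- Baseline gap g = .10 × .25 = 0.025 SD to .20 × .50 = 0.10 SD.
- If the gap persists to posttest, it cancels in the ANOVA group-by-time contrast.
- In the pretest-adjusted regression, (1 − r)g remains: .3 × .025 = 0.0075 SD to .5 × .10 = 0.05 SD.
- The adjusted SE at 60 per group is sqrt(1 − r²) × sqrt(2/60) = 0.158 (r = .5) or 0.130 (r = .7). The bias is thus 0.0075/0.130 = 0.06 SE to 0.05/0.158 = 0.32 SE. These ratios are slightly overstated, because unequal non-start leaves fewer than 60 in an arm.
- The simulated two-sided false-positive rate stays at about 5% to 6%.
- If non-start is equal across arms and unrelated to outcome, the bias is zero.

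**The case against.** The strongest reply is that nothing in the documents shows the arm reaching a CHW before the pretest. Pretest reminders are described identically for both arms, pretest pay is equal, and course access follows the pretest. The only arm-specific reminders belong to the period between surveys. The consent text is not available to this review, so silence about what CHWs are told cannot count against the plan. CHWs enter through an online link and the recruiting organisations do not learn who enrols, so recruiters cannot steer by arm. All of this stands. It narrows the route for steering to KDHRC's own handling of consent confirmations.

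A reader might infer that allocating before the pretest seriously inflates the false-positive rate. Such figures can be produced. Suppose one arm's pretest alone is distorted by 0.1 to 0.2 SD. The full shift then passes to the ANOVA and r times the shift (0.05 to 0.14 SD) to the regression. The nominal 5% becomes about 8% to 29% and 6% to 18%. The arithmetic is right, but it requires CHWs to know their arm and to distort only the pretest, and neither is documented. These figures illustrate an assumed worst case and do not support the seriousness of the point.

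A reader might also think that moving allocation costs nothing. It does affect the stated target. The Terminology section defines participants by completed consent, and the Protocol and SAP set 60 per group. CHWs who consent but never submit a pretest would have no group.

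None of this answers the contradiction between alternation and random assignment.

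**Conclusion.** The point holds for the method of allocation. The documented rule is alternation, which is neither random nor concealed and contradicts the Protocol's own description. That is certain from the text and needs no assumption. Its effect on the results cannot be sized from the documents.

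The timing of allocation is a secondary matter: a possible risk of unknown and probably small size. Under the assumed differential non-start, the false-positive rate barely moves. Changing the timing neither gains nor loses power for a given number of consents. The plan should be changed because the correction is simple, not because bias has been shown.

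**What to change.** In the Protocol's Approach and Methods sections, replace alternation with a computer-generated 1:1 sequence in permuted blocks of varying size. Conceal it from the staff who confirm consent and send reminders, and describe it in the same words in both places.

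As a low-cost addition, do one of the following:
- **Allocate at pretest submission**, reading the arm from the list just before course access is released, and report how many consented but did not submit a pretest.
- **Keep allocation at consent**, withhold the arm from CHWs and reminder staff until the pretest is in, and report pretest non-start by arm.

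Costs: generating and holding the list is a small task. Surveys and payments do not change. The maximum time from pretest link to end of posttest stays at 2 + 2 + 2 = 6 weeks per CHW.

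The first option has two further costs. Allocation must be prompt: the posttest clock starts at pretest completion, so each day of delay takes one of the 14 days available for the course. KDHRC already has to act at that point to release access. Also, the 60 per group in the Protocol (Participants and recruitment; Data Collection) and the SAP (Number of subjects) must be restated as up to 120 consented, with those who submit a pretest allocated 1:1. Neither option addresses losses after the pretest.
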